16. STUDY MEDICATION COMPLIANCE

Compliance to study medication will be presented for the SAF.

Document: CCI

Author: PPD

Version Number:

3.0

Version Date:

19May2023

CCI

Comparisons between treatments for treatment compliance will be performed using an ANOVA with treatment in the model.

16.1. DERIVATIONS

Treatment compliance for injection is based on the eCRF data will be calculated as:

$$\frac{\text{number of doses received} * 100}{\text{number of intended doses}}$$

The intended number of injections is 2 injections loading dose and 1 injection monthly for the next 2 months, resulting in a total of 3 monthly doses (4 syringes for injection). Thus, for participants in Safety analysis set who discontinued the study after less than 1 month treatment, the number of intended injections is 2.

The intended ODT dose is 1 tablet every other day starting on Day 1, thus the expected total number of tablets is the integer part of (the treatment duration in days plus 1 and divided by 2).

For participants in Safety analysis set who stayed on treatment for 1 month or longer, the number of intended injections is 2 plus the integer part of the treatment duration in months. Note for injections, if subject is compliant, no unused injections should be returned.

Compliance for ODT, based on the drug accountability data, will be calculated as the number of tablets taken (total dispensed – total returned) divided by the prescribed number of tablets expressed as a percentage, see calculations below.

Compliance (%) = (Actual total number of tablets / Expected total number of tablets) x 100
 For ODT, it is possible depending on the length of the treatment phase, some unused ODT may be returned. If the date of last dose is available, then the date of last dose of ODT should be used for determining the expected number of tablets.

For subjects without a date of last dose and no study drug returned and subjects report taking their study medication: it will be assumed that subjects took the medication as prescribed.

Comparisons between treatments for treatment compliance will be performed using an ANOVA with treatment in the model. For this analysis, partial dose (for example, a patient only got 1 injection instead of 2) will be considered as no dose received.

Document: **CCI**

Author: **PPD**

Version Number:

3.0

Version Date:

19May2023

CCI

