6.4. WINDOWING CONVENTIONS

The following describes assignment of visit windows to the following data for purposes of analysis:

- Screening lasts from 3 to 30 days, approximately.
- Eligibility is determined between a minimum of 30 days and a maximum of 40 days.
- For scheduling purposes, a month is 30 days.

See Section 18.1.1. for the derivation of diary time periods. No other assignment of visit will be done – visit as collected will be used.

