15. STUDY MEDICATION EXPOSURE

Patients will receive the investigational medicinal product (IMP) at the following planned time points:

- Beginning of Month 1 (Visit 3)
- Beginning of Month 2 (Visit 4)
- Beginning of Month 3 (Visit 5)

The number of Injections planned at each time point are as follows:

- Month 1 (Visit 3), two injections, count as 1 dose injected

Document: **CCI**

Author: **PPD**

Version Number:

3.0

Version Date:

19May2023

CCI

- Month 2 (Visit 4), one injection, count as 1 dose injected
- Month 3 (Visit 5), one injection, count as 1 dose injected

The following information will be recorded on the eCRF for each dose:

- Confirmation that the patient received the IMP (including reason if the IMP was not given)
- Date and time of administration

A summary and listing will be produced, for treatment phase (SP III), of the number and percentage of patients with 1 dose, 2 doses, or 3 doses injected. Comparisons between treatments for duration of IMP exposure will be performed using an ANOVA with treatment in the model. Number of patients with 1 dose, 2 dose, or 3 doses injected will be compared between treatment groups with Fisher's exact test. In addition, injections not administered will be listed.

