15.1. DERIVATIONS

The following will be derived from the information recorded on the eCRF:

For treatment phase (SP III), duration of exposure in days is calculated as treatment phase disposition date (i.e. study disposition date) – first date IMP administered +1 for subjects or one of the below if it is earlier:

For ODT:

Duration of exposure (days) = date of last study medication administration – date of first study medication administration + 1.

For Injection:

Duration of exposure (days) = date of last study medication administration – date of first study medication administration + 30.

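### SAP 16.1 divides doses by injections and states no maximum, so read literally a fully adherent participant scores below 100% on injection compliance

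*SAP*

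**What the plan says.** SAP 16.1 computes injection compliance from eCRF data as 100 × doses received / doses intended. The pieces that feed this ratio are:

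- **Numerator.** SAP 15 states "Month 1 (Visit 3), two injections, count as 1 dose injected", and counts the single injections at Visits 4 and 5 as one dose each. For the compliance comparison, SAP 16.1 says that a "partial dose (for example, a patient only got 1 injection instead of 2) will be considered as no dose received".
- **Full course.** Two injections, then one in each of the next two months, "resulting in a total of 3 monthly doses (4 syringes for injection").
- **Below one month.** For participants "who discontinued the study after less than 1 month treatment, the number of intended injections is 2".
- **One month or longer.** For participants who stayed on treatment, "the number of intended injections is 2 plus the integer part of the treatment duration in months".

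SAP 16.1 defines neither treatment duration nor month. Elsewhere, SAP 15.1 defines a duration of exposure as the disposition date minus "first date IMP administered +1 for subjects or one of the below if it is earlier"; the injection alternative is the last administration date minus "date of first study medication administration + 30". SAP 6.4 says "For scheduling purposes, a month is 30 days". Protocol 4.1.3 makes Visit 5 the last injection.

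**The concern.** The formula is in doses, but both rules that set its denominator by time on treatment are in injections, and no conversion is given. The loading pair is one dose above the line and two injections below it. In addition, the rule for one month or longer adds an injection for each completed month and does not stop after Visit 5.

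The reported injection compliance could therefore misdescribe adherence, and its value would depend on which sentence of the section is programmed. In a head-to-head trial a mean well below 100% invites questions about exposure that the data may not warrant.

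**Working it through.** **1. The plan's own total.** Injections: 2 + 1 + 1 = 4. Doses: 1 + 1 + 1 = 3. Both match the full-course figure in SAP 16.1, and with 3 doses as denominator an adherent completer scores 3/3 = 100%.

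**2. Units alone.** This needs no assumption about how duration is measured. For a participant who has taken every dose due:

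| Time on treatment | Doses received | Intended injections under the rule | Score |
|---|---|---|---|
| Below 1 month | 1 | 2 | 1/2 = 50% |
| 1 to below 2 months | 2 | 2 + 1 = 3 | 2/3 = 67% |
| Completer assigned the planned number | 3 | 4 | 3/4 = 75% |

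None reaches 100%.

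**3. Missing maximum alone.** Intended injections = 2 + floor(duration / month). Take a completer exactly on schedule, with Visit 5 at +60 days and Visit 6 at +90 days from first dose. Assume that duration is the SAP 15.1 exposure and that a month is 30 days:

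- duration = min(60 + 30, 90 + 1) = min(90, 91) = 90 days
- intended = 2 + floor(90/30) = 5, against 4 planned
- compliance in injections = 4/5 = 80%

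Because 16.1 fixes neither input, the same completer was run under four readings of duration and two month lengths (30.4375 days is an assumed calendar month):

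| Reading of duration | Days | Intended, 30-day month | Intended, 30.4375-day month |
|---|---|---|---|
| SAP 15.1, earlier of the two | 90 | 5 | 4 |
| To disposition, Visit 6 + 1 | 91 | 5 | 4 |
| Last − first injection + 30 | 90 | 5 | 4 |
| Last − first injection + 1 | 61 | 4 | 4 |

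The ±2-day visit windows also matter. Under the SAP 15.1 reading with a 30-day month, a fifth injection needs Visit 5 at +60 or later and Visit 6 at +89 or later. That is 3 × 4 = 12 of the 25 in-window day pairs. These are unweighted combinations, not shares of participants.

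**4. Both faults together.** Under the assumptions of step 3, 3 doses / 5 injections = 60%.

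**5. Who the below-one-month rule covers.** It is worded for participants who left the study. Protocol 7.1 keeps participants who stop study intervention in the study. A participant who stops treatment before one month but stays in the study falls under neither sentence: not the first, because the study was not discontinued, and not the second, because treatment lasted less than one month.

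**The case against.** The strongest reply is that the intent is plain. SAP 16.1 states a course of 3 doses or 4 syringes, presents the first time-based rule as following from it, and notes that a compliant participant returns no unused injections. The protocol ends injections at Visit 5. A sensible programmer would work in one unit and stop at 4, and an output in which every adherent participant falls below 100% would be noticed.

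Much of this stands for the maximum. A reader might infer that the SAP intends five injections, or that every completer will score 60%. The documents do not support that. The fifth injection appears only when an exposure definition that 16.1 does not cite is combined with a month length given for scheduling, and with a 30.4375-day month the on-schedule completer gets the planned 4 under all four readings.

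It does not answer the unit fault. A cap of 4 alone leaves 3/4 = 75%. Counting injections throughout departs from the written formula and from the partial-dose rule, which scores one of two loading injections as nothing.

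A reader might also infer that the denominator is unspecified for everyone who stops treatment early. That goes too far: the sentence for one month or longer already follows time on treatment, so the gap is only the group in step 5.

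**Conclusion.** The unit mismatch is wrong as written, not just short of detail. Two statements in one section give the same adherent completer 100% or 75%, and this rests on no assumption beyond the text. The missing maximum is real but conditional: 5 intended injections against 4 planned holds for an on-schedule completer if duration is the SAP 15.1 exposure and a month is 30 days.

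The impact is minor. It reaches one injection-compliance summary and its ANOVA. The same rule and the same double-dummy injection schedule apply in both arms, so the distortion is largely shared. A reader might suspect an effect on efficacy or on the deviation counts, but the efficacy analyses do not use this variable. The table of doses injected (SAP 15) and the skipped-dose deviation (SAP Appendix 3) are defined separately.

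**What to change.** Rewrite the injection rules in SAP 16.1 as follows:

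- **Unit and maximum.** Use one unit in numerator and denominator, and state the maximum: 3 doses or 4 injections.
- **Denominator.** Count the doses scheduled by target day (day of first dose, +30, +60) on or before the treatment disposition date, not the date of the last injection. A completer who misses the Visit 5 dose then scores 2/3 = 67% in doses (3/4 = 75% in injections). If counting ended at the last injection, the missed dose would disappear and the score would be 2/2 = 100%. SAP 15.1 equates the treatment-phase and study disposition dates, so say that for a participant who stops study intervention but stays in the study the date is that of treatment discontinuation.
- **Early injections.** Count any injection given before its target day as scheduled. Otherwise an injection at +28 with treatment ending at +29 gives 2/1 = 200% in doses. With the rule, the ratio is at most 100%.
- **Stopping before one month.** Apply that rule to participants who stop study intervention as well as to those who leave the study.

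Every in-window completer then has a denominator of 3 doses (4 injections), because the earliest Visit 6 is +88. Target days also fit Protocol 10.6, where injections keep their original schedule when the telephone visit is late.

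The cost is a short SAP paragraph and a small programming change. No new data should be needed, since SAP 9.1 already separates discontinuation of treatment from discontinuation of the study.

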## 6.3. Measures to Minimize Bias: Randomization and Blinding

This is a randomized, double-blind, double-dummy study.

Participants will be randomly assigned in a 1:1 ratio to receive study intervention. All participants will be centrally assigned to randomized study intervention using an IWRS. Before the study is initiated, the log in information and directions for the IWRS will be provided to each site. Participants will be stratified by baseline migraine frequency (<8 migraine headache days versus  $\geq 8$  migraine headache days). Randomization into 1 stratum may be discontinued at the discretion of the sponsor.

Study intervention will be dispensed to the participant by the designated unblinded site personnel at Visit 3 as summarized in SoA. The participants will receive enough tablets and syringes for the double-blind treatment period with the longest possible visit interval between visits.

Returned study intervention should not be re-dispensed to the participants.

Treatment assignments will remain blinded to investigators, study site personnel directly involved in participant assessments, and participants. To preserve the blinding of the study, a minimum number of Lilly personnel will see the randomization table and treatment assignments before the study is completed. Designated unblinded site personnel are responsible for receipt of study intervention shipments, dispensing study intervention, confirming treatment assignments, and receipt of any unused study intervention by the participant. Designated unblinded site personnel will not be involved in any clinical aspects of the study, including clinical evaluations and AE assessments. It is critical that the blind is maintained throughout the study (3 months).

As the last procedure of Visit 3, the unblinded site personnel will train the participant/caregiver on SC administration, which may include injecting the contents of the first syringe and supervising the participant/caregiver in the administration of the second injection. The unblinded

site personnel should also train the participant how to take the ODT and supervise the participant opening the blister pack and taking the first dose of ODT.

At the telephone visits at which an injection is to occur, self-injections are to occur on the same day as the scheduled telephone visit, prior to the start of visit procedures.

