### 7.2. Participant Discontinuation/Withdrawal from the Study

A participant may withdraw from the study:

- at any time at his/her own request
- at the request of his/her designee (for example, parents or legal guardian)

- at the discretion of the investigator for safety, behavioral, compliance, or administrative reasons
- if enrollment in any other clinical study involving an investigational product or enrollment in any other type of medical research judged not to be scientifically or medically compatible with this study
- if the participant, for any reason, requires treatment with another therapeutic agent that has been demonstrated to be effective for treatment of the study indication, discontinuation from the study occurs prior to introduction of the new agent.

Discontinuation is expected to be uncommon.

At the time of discontinuing from the study, if possible, an early discontinuation visit should be conducted, as shown in the SoA. See SoA for data to be collected at the time of study discontinuation and follow-up and for any further evaluations that need to be completed. The participant will be permanently discontinued from both the study intervention and the study at that time.

If the participant withdraws consent for disclosure of future information, the sponsor may retain and continue to use any data collected before such a withdrawal of consent. If a participant withdraws from the study, he/she may request destruction of any samples taken and not tested, and the investigator must document this in the site study records.

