		Any use of NURTEC (rimegepant) during SPII or III as a concomitant medication	Non-Programmable- Study Team identified	1) Stats will create the list of patients meet this IPD criteria. 2) Among those, the true IPDs will be manually added into non-programmable excel sheet.
		Taking prohibited CGRP antagonist (oral; except rimegepant) for >7 consecutive days during SPII or III	Non-Programmable- Study Team identified	1) Stats will create the list of patients meet this IPD criteria. 2) Among those, the true IPDs will be manually added into non-programmable excel sheet.
		Any use of a CGRP antagonist (monoclonal antibody) during SPII or III as a concomitant medication	Non-Programmable- Study Team identified	1) Stats will create the list of patients meet this IPD criteria. 2) Among those, the true IPDs will be manually added into non-programmable excel sheet.
Investigational Product	Medication not fit for use	Patient received drug that was declared "Not Fit for Use"	Non-programmable - Monitor identified	
	Dosing Error	Significant violations of study drug dosing	Non-programmable - Monitor identified and Study Team identified	1) Stats will create the list of patients who have incorrect dosing (not including skipped dose). 2) Monitors will identify other events not able to be captured by programming (such as switched IP packages) 3) Medical will review both lists and identify IPDs to be manually added into non-programmable Excel sheet.
	Injection Schedule	Skipped dose of study drug	Programmable - Stats	Will not be a protocol deviation if the patient's study intervention was withheld by the investigator for safety reasons

Document: CCI

Author: PPD

Version Number: 3.0

Version Date: 19May2023

Category	Subcategory	Study-specific	Source	Comments
Investigational Product	ODT schedule	Taking <80% or >120% of prescribed ODT doses	Programmable - Stats	Will not be a protocol deviation if the patient's study intervention was withheld by the investigator for safety reasons
	Unblinding	Unjustified un-blinding of patient treatment assignment	Non-programmable - Monitor identified	
Administrative/ Oversight	Suspected misconduct	Suspected Fraud	Non-programmable - Monitor identified	
	Patient privacy violation	Privacy Breach	Non-programmable - Monitor identified	This will only include those events which result in a full de-identification of the patient.

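### SAP 16.1 counts every unreturned ODT tablet as taken, which hides poor intake in late non-returners and produces false >120% deviations in early stoppers

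*SAP*

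**What the plan says.** SAP 16.1 defines ODT compliance as "the number of tablets taken (total dispensed – total returned) divided by the prescribed number of tablets expressed as a percentage". The expected number is one tablet every other day from Day 1, and its end point is set by this rule: "If the date of last dose is available, then the date of last dose of ODT should be used for determining the expected number". There is no cap and no category for tablets that were neither returned nor documented as taken. A separate branch reads "For subjects without a date of last dose and no study drug returned and subjects report taking their study medication: it will be assumed" that the participant dosed as prescribed.

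Protocol 6.3 fixes the supply: "The participants will receive enough tablets and syringes for the double-blind treatment period with the longest possible visit interval between visits". The Schedule of Activities shows dispensing at Visit 3 only, and return of unused drug at Visit 6 or early termination. For those who leave early, Protocol 7.2 makes the return visit conditional: "At the time of discontinuing from the study, if possible, an early discontinuation visit should be conducted".

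SAP Section 16 compares compliance between arms by ANOVA in the safety set. SAP Appendix 3 lists "Taking <80% or >120% of prescribed ODT doses" as a programmable important deviation. The only exemption is drug withheld by the investigator for safety reasons.

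Protocol 6.4 also requires a reconciled record of the ODT dispensed to and taken by each participant. The SAP formula does not refer to it.

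**The concern.** The numerator and denominator respond differently to early stopping. With nothing returned, the numerator stays at the full three-month supply, while the denominator shrinks to the days up to the last dose. Lost and discarded tablets count as swallowed. So the participants with the least reliable drug accountability receive either an unremarkable value near 100% or an impossible one.

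Two errors follow, mostly in different people. A late non-returner with poor intake looks fully adherent. An early stopper who returns nothing looks like someone who took too many tablets. An early stopper with poor intake suffers both.

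The ODT carries the active comparator. If galcanezumab is found superior, readers will ask whether rimegepant was taken as directed, and this pill count is the only ODT compliance measure that the SAP specifies.

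**Working it through.** The plan states no figure for this point, so there is none to reproduce. The SAP formula was applied directly.

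**Inputs**
- Expected tablets to last-dose day D: int((D + 1)/2), SAP 16.1.
- Tablets taken: dispensed minus returned, SAP 16.1.
- Flag limits: <80% and >120%, SAP Appendix 3.
- Tablets dispensed: not stated. Assumed range 46 to 56. The lower value just covers Day 92 (Visit 6 at Day 90 plus its 2-day allowance): int(93/2) = 46. The upper value allows for a more generous supply.

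**Nothing returned, last-dose date known**

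| Last dose | Expected | 46 dispensed | 56 dispensed |
|---|---|---|---|
| Day 30 | 15 | 306.7% | 373.3% |
| Day 46 | 23 | 200.0% | 243.5% |
| Day 60 | 30 | 153.3% | 186.7% |
| Day 76 | 38 | 121.1% | 147.4% |
| Day 90 | 45 | 102.2% | 124.4% |
| Day 92 | 46 | 100.0% | 121.7% |

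The >120% flag needs an expected count below dispensed/1.2. For 46 tablets, 46/1.2 = 38.3, so it fires up to 38 expected, that is, Day 76. For 56 tablets, 56/1.2 = 46.7, so it fires up to 46 expected, Day 92, which catches ordinary completers who return nothing.

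**Masking (46 dispensed, last dose Day 90)**
- True intake of 45, 36, 22 or 11 tablets out of 45 is 100%, 80%, 48.9% or 24.4%. With nothing returned, all four score 46/45 = 102.2%.
- Partial return masks partly. With 22 taken and 12 of the 24 leftovers returned, (46 − 12)/45 = 75.6%. With 36 taken and 5 of the 10 leftovers returned, (46 − 5)/45 = 91.1%.

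**With tablets correctly accounted for**
- Day 90, 22 taken: 22/45 = 48.9%, correctly flagged <80%.
- Day 30, all 15 taken: 15/15 = 100%, not flagged, instead of 306.7%.
- Day 30, 7 taken: 7/15 = 46.7%, instead of 306.7%.

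**Effect on the ANOVA (simulation, all inputs assumed)**
288 per arm; returners' compliance normal with SD 10 and mean 95% in the better arm; true difference 5 points; 46 tablets; non-returners return nothing and have a known last-dose date.

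| Non-returners per arm | Power, last dose Days 14–80 | Power, last dose Days 31–80 |
|---|---|---|
| None | about 100% | about 100% |
| 0.5% | 90% | above 99% |
| 1% | 78% | 98% |
| 5% | 27% | 68% |

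With equal true adherence and unequal non-return (Days 14–80), the spurious difference is about 4 points at 6% versus 3%, and about 1.5 points at 2% versus 1%.

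**The case against.** **The SAP never says that a missing return count is zero.** This is fair for a participant with no return visit. The formula rests on accountability data, and without a count it cannot be evaluated; on that case the SAP is silent. But a recorded zero return is covered by the stated rule, and an early stopper who attends the termination visit empty-handed still scores 46/15 = 307% at Day 30.

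**A reader might infer that non-returners generally score several hundred percent.** They do not. With 46 tablets, 200% or more needs a last dose by Day 46, and 300% or more by Day 30. Last doses on Days 47 to 76 give 121% to 192% (46/38 to 46/24), and completers score near 100%.

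**A reader might infer that a non-returner can never fall below 100%, or is always given 100%.** Neither holds. The imputation needs three conditions together: no last-dose date, nothing returned, and a report of taking the drug. Without a date or such a report, the denominator falls back on treatment duration, which SAP 15.1 allows to run to study disposition. A disposition on Day 120 would give 46/60 = 77%, below the lower limit.

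**A reader might infer that the ANOVA is largely disabled or biased between arms.** The documents give no non-return rate. They plan for dropout of no more than 10%, expect discontinuation to be uncommon (Protocol 7.2) and schedule drug return. Both arms take an ODT on the same schedule, so unequal non-return has no documentary basis. Only the range above can be shown.

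**Compliance matters little to the trial's conclusions.** This stands. Compliance enters no efficacy model and defines no analysis set, and the first sensitivity analysis in SAP 18.2.4 uses dosing dates rather than compliance.

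**Conclusion.** The concern holds in a limited form. The written rules give wrong values for participants who do not return leftover tablets, so this is more than missing detail. Near Day 90, a non-returner with a known last-dose date scores about 100% to 124% regardless of intake, and the <80% flag cannot fire. With 46 tablets, an early stopper who returns nothing is flagged above 120% for any last dose up to Day 76.

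These figures rest on the assumed supply of 46 to 56 tablets, a zero return and a recorded last-dose date. The frequency is unknown, so the ANOVA effect is conditional: for last doses on Days 14 to 80, power for a true 5-point difference is about 78% at 1% non-returners and 27% at 5%.

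The reach is the ODT compliance summary, its ANOVA, and the important-deviation table and listing. The documents do not support any reading that the primary or key secondary results are affected. The change is worth making because these outputs will be used to judge whether the comparator was taken, but it is not critical.

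**What to change.** In SAP 16.1:
- Take the number of tablets taken from the reconciled record of ODT dispensed and taken in Protocol 6.4.
- Use dispensed minus returned only where every dispensed tablet is accounted for. A recorded zero return is not enough by itself, because it still yields 307% for a Day-30 stopper.
- Otherwise set ODT compliance to missing. Apply this also to the branch that now imputes dosing as prescribed.
- Report the number and percentage of participants with unaccounted tablets by arm, beside the compliance summary.

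In SAP Appendix 3, do not raise the programmed <80% or >120% ODT flag from unaccounted tablets. Send those cases to blinded review.

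The cost is a short SAP revision and a programming condition, with no change to trial conduct. The downside is missing compliance for a few participants. The gain also depends on sites completing the 6.4 record independently: where it only restates the return count, the missing-value rule must govern.
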